6.2.3 Follow-up period and trial completion

For all patients who had at least one dose of trial medication, the follow-up visit will be performed as described in section 3.3.4.1 and 3.3.4.2.

If the last day of trial drug intake is different from the day prior to the EOT visit, the date of the last day of trial drug intake will be used for calculation of the FUP/EOS visit date.

Patients who finish the randomized treatment period according to the protocol, will return to the clinic for the end of study (EOS) Visit 11. Trial completion is defined as patients having reached the EOS visit within the specified window per the Flow Chart 1. The trial completion page in the eCRF has to be entered.

For all randomized patients, termination of trial medication and trial completion must be recorded on the corresponding eCRFs.

Should it be not possible for the patient to attend a follow up visit at the trial site, a visit out of time window should be performed as soon as possible; if a visit at the site is not possible at all, at least a phone contact should occur at the scheduled follow-up visit time point (please refer to section 3.3.4.1 and 5.4.6.2.1).

Page 94 of 148

Proprietary confidential information © 2023 Boehringer Ingelheim International GmbH or one or more of its affiliated companies

7. STATISTICAL METHODS AND DETERMINATION OF SAMPLE SIZE

7.1 NULL AND ALTERNATIVE HYPOTHESES

This trial is designed to assess the effects of BI 1358894 and placebo on patients with PTSD.

There will be no formal hypothesis testing performed. Inference concerning the efficacy of BI 1358894 will be assessed based on the estimated mean difference(s) between the treatment and placebo arm on the change from baseline to Week 8 in CAPS-5 total score, as well as other efficacy endpoints.

7.2 PLANNED ANALYSES

7.2.1 General considerations

The following patient analysis sets are defined for this trial:

- Full Analysis Set (FAS): includes all randomized patients who received at least one
 dose of trial medication during the trial and had a baseline and at least one postbaseline observation for the primary or secondary endpoints. The FAS is used for
 efficacy analyses and patients in FAS are analysed under the randomized trial
 medication.
- Treated Set (TS): includes all patients who signed informed consent and were treated with at least one dose of the trial medication. Patients in TS are analyzed under the actual trial medication received at randomization. The TS is used for safety analyses as well as demographics and baseline characteristics.

Data from patients who were screened but not randomized will be listed but not included in any summary or inferential statistics.

In general, baseline values are the last measurements taken prior to the first administration of trial medication at randomization (Visit 2), (see Flow Chart 1). Further details (e.g., the handling of randomized patients that receive the wrong treatment) will be provided in the TSAP.

7.2.2 Handling of Intercurrent Events

In the analyses of the primary endpoint, the following intercurrent events (ICEs) are of interest:

- 1. Change in background CNS active medication (e.g., non-SSRI antidepressant, anxiolytics)
- 2. Change in pharmacological therapy (SSRI)
- 3. Change in drug test result from negative to positive (Cannabis, Benzodiazepine, Barbiturates, Opiates, Cocaine, Amphetamines, Methadone, PCP)
- 4. Change in non-pharmacological therapy trauma-focused psychotherapy

Proprietary confidential information © 2023 Boehringer Ingelheim International GmbH or one or more of its affiliated companies

- 5. Change in non-pharmacological therapy all other cognitive/behavioral therapy (CBT) (e.g., any other kind of psychotherapy, nicotine withdrawal therapy, diet, etc.)
- 6. Withdrawal of study medication due to investigator assessed drug-related adverse events (e.g., headache)
- 7. Withdrawal of study medication due to perceived lack of efficacy or disease worsening
- 8. Withdrawal of study medication due to other adverse events
- 9. Withdrawal of study medication due to any other reasons

Table 7.2.2:1 Handling rules for Intercurrent events

	ICE	Primary Estimand	Supplementary Estimand
Handling rules for ICEs	1-4	Treatment policy	Treatment policy
	5	Treatment policy	Treatment policy
	6-7	Hypothetical	Treatment policy
	8-9	Hypothetical	Hypothetical

The primary estimand estimates the treatment effect when changes to background CNS active medication, pharmacological SSRI therapies and non-pharmacological therapies (ICEs 1-5) are considered to be part of the treatment effect, but changes to randomized treatment (ICEs 6-9) are not considered to be part of the treatment effect of interest. ICEs are therefore handled by a hybrid estimand that combines the treatment policy and hypothetical approaches, where ICEs 1-5 are handled using the treatment policy approach, and measurements taken after the occurrences of these ICEs are included in the primary analysis; ICEs 6-9 are handled using the hypothetical approach, and measurements after their occurrences are therefore censored in the primary analysis.

Page 96 of 148

Proprietary confidential information © 2023 Boehringer Ingelheim International GmbH or one or more of its affiliated companies

Regardless of the occurrence of ICEs, every attempt will be made to follow all patients until the end of the planned study period.

7.2.3 Primary objective analyses

The primary analysis of the primary efficacy endpoint uses the Full Analysis Set. Intercurrent events are handled as specified in Section 7.2.2 above and missing data as a result from the strategy (including both actual missing outcomes and excluded outcomes) will be handled using a mixed effects model with repeated measures (MMRM) under the assumption of missing at random (MAR). For change from baseline to Week 8 in CAPS-5 total score, a restricted maximum likelihood (REML) based approach using MMRM will be conducted to compare the adjusted mean between BI 1358894 125mg QD vs. placebo QD. The MMRM includes the fixed categorical effects of treatment at each visit, fixed categorical effects of the stratification factor of presence of significant childhood trauma (yes vs. no), and the fixed continuous covariates of time since index event (in years) and baseline CAPS-5 total score at each visit. Patient is treated as random effect. Visit will be treated as the repeated measure with an unstructured covariance structure used to model the within-patient measurements.

The Kenward-Roger approximation will be used to estimate denominator degrees of freedom and adjust standard errors. The point estimates of the adjusted mean difference between treatment arms at each visit, together with the corresponding two-sided 95% confidence intervals and p-values will be presented. The p-values and 95% confidence intervals are considered descriptive statistics. The primary treatment comparison will be the contrast between treatment and placebo at Week 8.

Procedures to follow if the MMRM analysis fails to converge will be described in the Trial Statistical Analysis Plan.

7.2.4 Secondary objective analyses

For the continuous efficacy endpoint of change from baseline on the PTSD Checklist for DSM-5 (PCL-5) total score at Week 8, the same strategy for handling the intercurrent events in the primary estimand analysis and a similar MMRM analysis used for the primary efficacy endpoint will be conducted to obtain the adjusted mean treatment effect between BI and placebo in terms of change from baseline to Week 8. This MMRM model includes the discrete fixed effects of treatment at each visit, fixed categorical covariate of the stratification factor of presence of significant childhood trauma (yes vs. no), and continuous fixed effects

Page 97 of 148

Proprietary confidential information © 2023 Boehringer Ingelheim International GmbH or one or more of its affiliated companies

of time since index event (in years) and the corresponding baseline endpoint value at each visit. Visit will be treated as the repeated measure with an unstructured covariance structure to model the within-subject measurements. Subjects will be considered as a random effect. The primary treatment comparison is the contrast between treatment and placebo at Week 8.

A logistic regression adjusted for treatment and stratification factor of presence of significant childhood trauma (yes vs. no) will be used for binary endpoints.

7.2.6 Safety analyses

Adverse events will be coded using the Medical Dictionary for Drug Regulatory Activities (MedDRA) coding dictionary. Standard BI summary tables and listings will be produced.

All treated patients will be included in the safety analysis and will be summarized under the actual trial medication received at randomization. In general, safety analyses will be descriptive in nature and will be based on BI standards. No hypothesis testing is planned.

Statistical analysis and reporting of adverse events will concentrate on treatment-emergent adverse events. To this end, all adverse events occurring between the start of treatment and the end of the residual effect period will be considered 'treatment-emergent'. The residual effect period is defined as 28 days after the last dose of trial medication. Adverse events that start before first drug intake and deteriorate under treatment will also be considered as 'treatment-emergent'.

Frequency, severity, and causal relationship of adverse events will be tabulated by system organ class and preferred term after coding according to the most updated version of the MedDRA at the time of reporting.

Frequency tables for all adverse events, protocol-specified adverse event of special interest (AESI), serious adverse event (SAE), adverse event leading to death, adverse event leading to discontinuation, investigator assessed drug-related adverse event and serious related adverse event will be generated for treatment-emergent adverse events. In addition, summary statistics and descriptive analyses will be conducted for other safety parameters that are assessed using dedicated scales, including suicidality as assessed by C-SSRS.

Page 98 of 148

Proprietary confidential information © 2023 Boehringer Ingelheim International GmbH or one or more of its affiliated companies

Laboratory data will be analysed both quantitatively as well as qualitatively. The latter will be done via comparison of laboratory data to their reference ranges. Values outside the reference range as well as values defined as clinically relevant will be highlighted in the listings. Treatment groups will be compared descriptively with regard to distribution parameters as well as with regard to frequency and percentage of patients with abnormal values or clinically relevant abnormal values.

Vital signs, physical examinations, or other safety-relevant data observed at screening, baseline, during the trial and at the end-of-trial evaluation will be assessed with regard to possible changes compared to findings before start of treatment.

For more details, please refer to the TSAP.

7.2.7 Other Analyses

7.2.8 Interim Analyses

An interim analysis is planned when the 120th evaluable patient completes the preplanned treatment period. Here, an evaluable subject is one that has remained in the study, and has at least one change from baseline CAPS-5 severity score.

The purpose of this interim analysis is for internal planning of the PTSD indication with BI 1358894. PoC could be established and the trial may be stopped early if at the interim analysis an impressive standardized effect size is observed. The decision to stop or continue the trial will be made by BI based on the totality of evidence - to also include observations from secondary objectives and the safety profile. An independent team will be formed to perform this analysis. Details will be specified in an interim analysis logistic plan.

The same MMRM model and estimands used on the primary endpoint, will be used for this interim analysis. When the 120th evaluable patient has completed the preplanned treatment period, the analysis will be performed on the change from baseline to Week 8 in CAPS-5. Based on this observed standardized effect size of the change in CAPS-5 at Week 8 at interim, along with evidence from secondary objectives, as well as the observed safety profile, a team decision will be made to either stop the trial early for efficacy, and potentially claim the achievement of PoC in this indication, or continue enrolling patients until the maximum recruitment target of 200 evaluable patients is reached (assuming a drop-out rate of 30%, this is equivalent to a total sample size of 286 randomized patients, please refer to

Page 99 of 148

Proprietary confidential information © 2023 Boehringer Ingelheim International GmbH or one or more of its affiliated companies

Section 7.5 for more details on the sample size justification). Detailed efficacy boundary at interim will be specified in a separate document.

During the conduct of the interim analysis, recruitment into the trial will continue. If the trial is stopped at interim, there will be a final analysis of the complete data set that will include all the patients that were enrolled during the conduct of the interim analysis period. In order to support the double-blinded conduct of the trial, the trial team will be kept blinded to the individual patients' treatment group assignment at interim. A separate team will perform the interim analysis. Details will be specified in a separate logistic plan.

More details about the interim analysis and final analysis will be specified in the TSAP and (or) in the interim logistic plan.

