3. DESCRIPTION OF DESIGN AND TRIAL POPULATION

3.1 OVERALL TRIAL DESIGN

This is a Phase II, 8-week-treatment, multicenter, randomized, double blind, placebo-controlled, parallel-group trial in patients with Post-Traumatic Stress Disorder (PTSD). In total, approximately 286 male and female patients with PTSD meeting the entry criteria are planned to be randomized into this trial.

V = Visit, W = Week, EOT = End of Treatment, EOS = End of study, ☎ = Telephonic Visit

Figure 3.1: 1 Trial design

Patients are enrolled into the trial after informed written consent has been obtained. Eligible patients will be randomized to double-blind treatment with either placebo (approx. n=143) or BI 1358894 at 125 mg QD (approx. n=143). Total treatment duration will be eight weeks, refer to Figure 3.1: 1.

After the completion of the 8-week double-blind treatment period or following early discontinuation of the trial at any timepoint, patients will complete the 4-week follow-up period with the end of study (EOS) visit. All (S)AEs, including those persisting after individual patient's end of study must be followed up until they have resolved, have been assessed as "chronic" or "stable", or no further information can be obtained. Individual patient participation is concluded when the patient has completed their last planned visit (end of study visit) (refer to sections 3.3.4.1 and 3.3.4.2).

An interim analysis is planned when the 120th evaluable patient completes the Week 8 visit. The purpose of this interim analysis is for internal planning of the PTSD indication with BI 1358894. Please refer to section 7.2.8

Page 44 of 148

Proprietary confidential information © 2023 Boehringer Ingelheim International GmbH or one or more of its affiliated companies

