7.5 DETERMINATION OF SAMPLE SIZE

It is planned to randomize a maximum of 286 patients in this trial, since this sample size is considered sufficient to provide a reasonable chance to achieve the aims of this trial (Please refer to Table 7.5: 1 for more details). Assuming an early study drop-out rate of 30%, this is equivalent to a total of 200 evaluable patients.

An interim analysis to potentially stop the trial due to efficacy will take place when the 120th evaluable patient (about 172 patients randomized, assuming an early drop-out rate of 30%) has completed the 8-week treatment duration. If the trial is not stopped at interim, then patient enrolment will continue to the pre-planned maximum of 286 patients (200 evaluable patients).

Proprietary confidential information © 2023 Boehringer Ingelheim International GmbH or one or more of its affiliated companies

The sample size calculation is based on a target SES of BI 1358894 vs. placebo of 0.35 for the primary endpoint. Recent research on drugs for the PTSD indication suggest that an estimated standardized ES around 0.38-0.53 could be expected (assuming equal variances of the treatment and the placebo groups) [R21-1623]. The assumed SES of 0.35 is based on the expectation that BI 1358894 has competitive efficacy with other drugs under development.

Based on these sample sizes, the probabilities of observing a (1) ES >= 0.5 at interim, and (2) ES < 0.5 at interim, and ES < 0.25, between 0.25 and 0.32, or >= 0.32 at the final stage with 200 evaluable patients are presented in Table 7.5: 1. The estimated ES is between treatment and placebo on the change from baseline to Week 8 in CAPS-5 total score. In addition, the overall probability of observing an ES >= 0.5 at interim or observing a standard ES of at least 0.32 at the final stage are presented in Table 7.5: 1.

Table 7.5: 1 Probabilities of observing a standardized ES at different stages of the study for treatment relative to placebo under different scenarios (60 and 100 evaluable patients per arm at interim, and at final analysis stage, respectively).

			True stand	dardized E	ZS	
Probabilities	0.53	0.46	0.35	0.25	0.15	0.1
P(observed SES >= 0.5 at interim)	0.579	0.422	0.204	0.081	0.028	0.015
P(obs SES < 0.5 at interim & final obs SES >= 0.32)	0.356	0.424	0.395	0.241	0.093	0.048
P(obs SES < 0.5 at interim & final obs ES < 0.25)	0.024	0.066	0.230	0.488	0.755	0.854

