7.9.3 Interim Analyses

An interim analysis is planned when the 120th evaluable subject completes the planned treatment period. An evaluable subject is one that has remained in the study, and has at least one change from baseline CAPS-5 severity score. The purpose of this interim analysis is for internal planning of the PTSD indication with BI 1358894. PoC will be evaluated. The decision to stop or continue the trial will be made by BI based on the totality of evidence - to also include observations from secondary objectives and the safety profile. An independent team will be formed to perform this analysis. Details on whom has access to unblinded data will be specified in an interim analysis logistic plan. Table 7.9.3:1 provides the scope of analysis for the interim analysis package.

	Table 7.9.3:1	Interim Analysis Package
--	---------------	--------------------------

Demographics.	Disposition and Baseline conditions			
	Baseline demographic tables (include HA/migraines)			
	2. Comorbidities			
	 Concomitant medications – Background therapies 			
2	4. Disposition Table			
Primary and se	ry and secondary endpoints			
	5. Change from baseline in Clinician-Administered PTSD Scale for DSM-5 (CAPS-5) total severity score at Week 8			
(5. Response defined as $\geq 30\%$ CAPS-5 reduction from baseline at Week 8			
,	7. Response defined as \geq 50% CAPS-5 reduction from baseline at Week 8			
8	 Change from baseline on the PTSD Checklist for DSM-5 total score at Week 8 			
Standard safety	,			
9	Overall summary of patients with AEs			
	0. Frequency of patients with AEs			
	11. Frequency of patients with AEs leading to drug discontinuation			
	12. Frequency of patients with serious AEs			
	13. Frequency of patients with AEs leading to death			
	4. Suicidality as assessed by C-SSRS			
	5. AEs suggestive of abuse potential			

2.0030 c42059532-01 Proprietary confidential information © 2023 Boehringer Ingelheim International GmbH or one or more of its affiliated companies.

Explorato	ory
	16. Change from baseline in Pittsburgh Sleep Quality Index (PSQI) global scores over time
	17. Change from baseline in the Difficulties in Emotion Regulation Scale (DERS-16) total score at Week 8
	18. Change from baseline in the State Trait Anxiety Inventory (STAI) State and Trait version at Week 8. Specifically, the change from baseline in the STAI- S and STAI-T at Week 8.
	19. Change from baseline in CGI-S at Week 8

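### The definition of an evaluable patient is not tied to the primary estimand, so the 60 and 100 Week 8 outcomes per arm behind Table 7.5:1 are not guaranteed

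*Protocol*

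**What the plan says.** **Who counts.** Protocol 7.2.8: "an evaluable subject is one that has remained in the study, and has at least one change from baseline CAPS-5 severity score". SAP 7.9.3: "An evaluable subject is one that has remained in the study, and has at least one change from baseline CAPS-5 severity score". Neither text asks for a Week 8 score or for the patient to be on drug.

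**Who stays.** Protocol 3.3.4 and 3.3.4.1 ask patients who stop drug early to keep attending visits. Section 6.2.2 makes their Week 8 visit their Visit 10.

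**Whose score is used.** Protocol 7.2.2 states that "ICEs 6-9 are handled using the hypothetical approach, and measurements after their occurrences are therefore censored in the primary analysis"; these events are the withdrawals from study medication. SAP 6.3 keeps data up to 7 days after the last dose. Protocol 7.2.8 applies the same model and estimands at the interim.

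**What was planned for.** Table 7.5:1 is computed for "60 and 100 evaluable patients per arm at interim, and at final analysis stage, respectively". The link to the number randomised is in 7.5: "Assuming an early study drop-out rate of 30%, this is equivalent to a total of 200 evaluable patients".

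**When the interim happens.** Protocol 3.1: "An interim analysis is planned when the 120th evaluable patient completes the Week 8 visit". Protocol 7.2.8 and SAP 7.9.3 instead refer to that patient completing the planned treatment period, and Protocol 7.5 to the 8 weeks of treatment having been completed.

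**The concern.** Two groups can meet the definition without giving a Week 8 outcome to the primary analysis: patients who stop drug more than 7 days before Week 8 and stay in follow-up, and patients who remain in the study with only a Week 4 CAPS-5. The better the retention after drug stop, the more of the first group there are, and the earlier the count of 120 is reached relative to usable data.

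The three trigger wordings do not settle whether the first group counts. Completing the Week 8 visit includes them. Completing the treatment period can be read to exclude them. Two teams could therefore run the interim at different times.

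At stake are the operating characteristics in Table 7.5:1. With fewer outcomes the observed standardised effect size (SES) is noisier, so a weak drug passes a fixed threshold a little more often and a strong drug a little less often. The interim look can end the trial with a claim of proof of concept.

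**Working it through.** **Inputs.** From Protocol 7.5: 60 and 100 evaluable patients per arm; thresholds of SES 0.5 at interim and 0.32 at final; true SES of 0.53, 0.35 (the target) and 0.10; drop-out 30%. Allocation is 1:1. The share f of evaluable patients without a retained Week 8 score is not in the documents and is assumed here.

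**Step 1: reproduce the plan's figures.** Take the observed SES with n per arm as normal, with mean equal to the true SES and variance 2/n. The final look includes the interim patients, so the covariance of the two looks is 2/100. The standard error is √(2/60) = 0.183 at interim and √(2/100) = 0.141 at final. The overall probability (at least 0.5 at interim, or at least 0.32 at final) is then:

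| True SES | Table 7.5:1 | Recomputed |
|---|---|---|
| 0.53 | 0.935 | 0.933 |
| 0.35 | 0.599 | 0.591 |
| 0.10 | 0.063 | 0.064 |

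The largest difference in any cell of the table is 0.014 (0.579 stated, 0.565 recomputed). The randomised numbers also reproduce: 200/0.7 = 285.7, so 286, and 120/0.7 = 171.4, so 172. The arithmetic is right. It treats every evaluable patient as a Week 8 outcome.

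**Step 2: upper bound on the loss.** Suppose patients without a retained Week 8 score contribute nothing, so n becomes n(1 − f) at both looks and the standard error grows by 1/√(1 − f).

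| f (assumed) | Per arm, interim / final | SE ratio | Overall, SES 0.53 | SES 0.35 | SES 0.10 |
|---|---|---|---|---|---|
| 0 | 60 / 100 | 1.000 | 93.3% | 59.1% | 6.4% |
| 10% | 54 / 90 | 1.054 | 92.3% | 58.8% | 7.5% |
| 20% | 48 / 80 | 1.118 | 91.1% | 58.6% | 8.9% |
| 30% | 42 / 70 | 1.195 | 89.7% | 58.3% | 10.6% |

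For the interim threshold alone at true SES 0.10, the probability goes from 1.4% to 1.9% (f = 10%) and 2.5% (f = 20%).

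**Step 3: allow for Week 4 data.** The model also uses on-drug Week 4 scores. If all these patients have one, and r is the correlation between Weeks 4 and 8 (assumed 0.5 to 0.7), the effective n is n / [(1 − r²)/(1 − f) + r²].

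- At f = 10% and r = 0.5: 60 / (0.75/0.9 + 0.25) = 60/1.083 = 55.4 at interim. With r = 0.7 it is 56.8.
- At f = 20%: 50.5 to 53.2 at interim and 84.2 to 88.7 at final.

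Study drop-outs outside the count add more. At interim there are (172 − 120)/2 = 26 per arm. If half of them (13, assumed) have an on-drug Week 4 score, then 73 patients per arm have Week 4 data and the effective n is 1 / [(1 − r²)/n₈ + r²/73], where n₈ is the number with a retained Week 8 score.

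- At f = 10% (n₈ = 54): 57.8 for r = 0.5 and 61.9 for r = 0.7.
- At f = 20% (n₈ = 48): 52.5 and 57.7.

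Across these assumptions the effective interim n per arm is about 55 to 62 at 10% and 50 to 58 at 20%.

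**Step 4: what the 30% covers.** Step 2 puts f on top of a 30% loss, so the share of randomised patients without a usable Week 8 score is 1 − 0.7 × 0.9 = 37% at f = 10% and 1 − 0.7 × 0.8 = 44% at f = 20%. If instead the 30% includes everyone who stops drug, 286 × 0.7 = 200 patients keep a Week 8 score once all 286 are randomised. The interim count can still be reached early on that reading. If half of those who stop drug stay in the study (assumed), 85% of randomised patients are evaluable, and f = 0.15/0.85 = 17.6%. The 120 evaluable patients then include 120 × (1 − 0.176) = 99 with a retained score.

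**The case against.** A reader might infer that the stated numbers will not be reached, or that the plan's false-positive risk is materially understated. The documents do not support either, for these reasons.

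- **The share is unknown.** No rate is given for stopping drug while staying in the study. If nobody does so and nobody misses Week 8, the shortfall is zero. A stop within 7 days of the Week 8 assessment does not lose the score under the SAP.
- **The trigger can be read more favourably.** Section 6.2.2 separates patients who complete 8 weeks of treatment from those who stop and continue visits. On that usage, completing the planned treatment period excludes off-drug patients from the interim count, and only the sentence in 3.1 plainly includes them. This stands as a plausible reading. The definition of evaluable beside it in 7.2.8 does not say so.
- **The 30% may already cover drug discontinuation.** It is called study drop-out only once; elsewhere it is simply drop-out. If it covers both, and all 286 are randomised as 7.5 plans, about 200 retained Week 8 scores remain at the final analysis whatever the definition. However, 7.2.8 states the recruitment target as 200 evaluable patients, so the definition also matters there.
- **The upper bound is pessimistic.** The model uses Week 4 scores, and at f = 10% the planned 60 may be nearly met. At true SES 0.10 the shift at f = 10% is 1.1 points, smaller than the 1.4-point gap between stated and recomputed values in one cell of the table.
- **There is no binding test.** Protocol 7.1 excludes formal hypothesis testing. Section 7.2.8 bases the interim decision on all the evidence and leaves the efficacy boundary to a separate document. The 0.5 and 0.32 cut-offs are those used for the table's probabilities. No alpha level is breached.

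These points limit the size. They do not reconcile the definition with the estimand or the trigger wordings with each other.

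**Conclusion.** The mismatch is in the text: the rule that counts patients towards 120 and 200 is looser than the rule that decides whose Week 8 score enters the primary analysis. The 60 and 100 per arm are therefore not guaranteed; whether they are missed cannot be told from the documents.

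The likely effect is modest. With an assumed 10% or 20% of counted patients lacking a retained Week 8 score, and no credit for Week 4 data, the overall probability moves by 1.1 or 2.5 points at true SES 0.10, by −1.0 or −2.2 points at 0.53, and by at most half a point at the target of 0.35. With Week 4 data the effect is smaller. This is a cheap improvement to the plan, and it does not undermine the design.

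**What to change.** - In Protocol 3.1, 7.2.8 and 7.5 and in SAP 7.9.3, define an evaluable patient as one with a baseline CAPS-5 and a Week 8 CAPS-5 that the primary estimand retains, that is, taken no later than 7 days after the last dose.
- Trigger the interim at the 120th such patient, with the same wording in all four places.
- Keep the maximum of 286 randomised patients.
- State whether the 30% covers drug discontinuation as well as study drop-out. If it does not, restate the expected evaluable number and rerun Table 7.5:1.

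**Cost.** The change needs a wording amendment and possibly one rerun of the table. If 10% of patients who remain in the study lack a retained score, in addition to 30% drop-out, the interim comes at about 120/(0.9 × 0.7) ≈ 190 randomised instead of 172. On the same assumption the expected final number is 286 × 0.7 × 0.9 ≈ 180 instead of 200.
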